The generation of knowledge regarding the usefulness of metformin in this specific group of patients can lay the groundwork for research on the effect of this drug in solid tumors and other pediatric neoplasms.

HYPOTHESIS

If metformin is added to standard chemotherapy during the remission induction phase in Mexican adolescents with newly diagnosed ALL, then it will decrease the level of ABCB1/MDR1 gene mRNA expression and increase AMPK expression levels, at the end of this treatment period.

OBJECTIVES

General:

- To evaluate the efficacy of metformin in modifying ABCB1 and AMPK gene expression in adolescents diagnosed with ALL during the remission induction phase.

Specific

- To describe the expression levels of ABCB1/MDR1 and AMPK genes in adolescents with ALL at diagnosis and in healthy controls.
- To compare the expression levels of ABCB1/MDR1 and AMPK genes at diagnosis and at the end of induction in adolescents with ALL treated with conventional chemotherapy and those additionally treated with metformin.
- To compare overall and disease-free survival in adolescents with ALL treated in relation to ABCB1/MDR1, and AMPK gene expression.
- To compare overall and disease-free survival in adolescents with ALL treated with conventional chemotherapy with those treated with conventional chemotherapy plus metformin.

METHODOLOGY

Type and design of study

Type of study: randomized clinical trial

Study design: analytical, experimental, longitudinal and prospective study.

Population

The population to be studied are patients with newly diagnosed ALL between 10 and 21 years.

Eligible population: patients with newly diagnosed ALL between 10 and 21 years old, diagnosed at the Hospital General de México "[name]" from February 2021 to December 2023.

Inclusion, exclusion and elimination criteria

- Inclusion criteria:
 1. Patients aged between 10 and 21 years with a new diagnosis of ALL at the Hospital General de México, [name].
 2. Patients and legally authorized person who sign the informed consent.

- Exclusion criteria:
 1. Patients with antineoplastic treatment prior to admission.
 2. Patients with Down syndrome.

- Elimination criteria:
 1. Patients who abandon treatment for more than a few weeks.4
 2. Patients who withdraw informed consent

Sample size

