To calculate the sample size, we used data from the publication by Ramos Peñafiel⁶³, where a decrease in the expression pattern of ABCB1 gene expression from high to low expression after metformin administration was 50%.

The sample size calculation was based on the formula for estimating a proportion, with a confidence level of 95% and a precision of 5%:

$$n = \frac{Z_{\alpha}^2 * p * q}{d^2}$$

A sample number of 8 patients in each group is obtained, assuming a loss of 20%, 10 patients are calculated for each group.

Definition of the variables to be evaluated and how they are to be measured

Variable	Conceptual Definition	Unit of measurement	Type of variable	Coding
Age	Time elapsed in years since birth.	Years	Quantitative	Not applicable

Gender	Male or female phenotype of the person.	Male/female	Qualitative Dichotomous	0: male 1: female
Leukocyte count at diagnosis	Number of total leukocytes reported on complete blood count at diagnosis.	X10/ml ³	Quantitative	Not applicable
Hemoglobin at diagnosis	Measurement of the amount of oxygen transport protein reported in initial complete blood count.	g/dL	Quantitative	Not applicable
Platelet count at diagnosis	Measurement of the number of platelet fragments produced by the megakaryocytes, reported in the initial complete blood count.	X10/ml ³	Quantitative	Not applicable
Immunophenotype of leukemia lymphoblastic	Cellular variant of acute lymphoblastic leukemia	B/ T	Qualitative dichotomous	0: strain B 1: lineage T
Cytogenetic alterations	Alterations in the genetic structure of leukemic cells.	None/ t(9;22)/ t(12,21)/ t(4,11), other	Qualitative polytomous	0: none 1: t(9;22), 2: t(12,21) , 3: t(4,11), 4: other
MDR-1 and AMPK gene expression.	Amplification of gene expression by RT-PCR	No expression / low expression / high expression expression	Qualitative polytomous	0: not expressed 1: high expression 2 low expression
Pre-phase response with prednisone	Decrease in total peripheral blood blast count less than 1000 after 7 days of steroid (day 0)	Present/absent	Qualitative dichotomous	0: Yes 1: No
Morphological status at day +14	Presence of blasts in bone marrow sample per day +14 referral induction	M1, M2, M3	Qualitative polytomous	0: M1 1: M2 2: M3
Morphological response at the end of induction	Presence of blasts in the bone marrow aspirate at the completion of remission induction phase.	M1, M2, M3	Qualitative polytomous	0: M1 1: M2 2: M3

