The Kolmogorov-Smirnov test will be performed for continuous variables to determine if they have normal distribution; if they have normal distribution, both groups will be analyzed by means of the t-student test; if they do not have normal distribution, the chi-square test, Fisher's exact test and Mann Whitney U test will be used for the bivariate analysis. To compare the expression of ABCB1/MDR1 and AMPK genes at the time of diagnosis and at the end of induction, McNemar's test will be used.

For the calculation of the overall and disease-free survival function, the Kaplan Meier survival test will be used for both groups and the differences between groups will be analyzed by means of the log Rank test, both for overall and disease-free survival. Similarly, the overall and disease-free survival function will be analyzed with the Kaplan Meier test and log rank for ABCB1/MDR1 and AMPK gene expression.

ETHICAL AND BIOSAFETY ASPECTS

According to the General Health Law regarding research on human subjects, this protocol is considered a higher than minimal risk research, since randomized methods of assignment to therapeutic schemes are used.

This protocol takes into account the Mexican General Health Law regarding the provision of health care services and health research, as well as national and international ethical standards.

This study will be carried out with strict observance of recognized scientific principles and respect and confidential handling of the data obtained. The security mechanisms to maintain the ethical aspects of this study are:

1. Review of this protocol by the research and ethics committees of the Hospital General de México "[name]".
2. All information obtained in this study will be made available to the Ethics and Research Committees.
3. The confidentiality of the study information is assured, as well as the identity of the patients. The identification data of the participants will be codified, assigning a consecutive participation number. The identification information and the relation between the identification numbers and the data obtained will be known only to the participating investigators and will be preserved confidentially in electronic media.
4. There will be no charge for the study, nor will there be any consistency for participation in this study. Refusal to participate in the study will not influence the patient's treatment or clinical care.

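### The proportion the trial is sized on, ABCB1 moving from high to low, has no stated denominator, cannot be estimated to within 5 points by 8 per group, and is not a planned estimate

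*Combined protocol and SAP*

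**What the plan says.** All places are in the combined protocol and SAP.

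- **Sample size.** The planning value comes from a publication "where a decrease in the expression pattern of ABCB1 gene expression from high to low expression after metformin administration was 50" per cent. The method is stated as follows: "The sample size calculation was based on the formula for estimating a proportion", "with a confidence level of 95% and a precision of 5" per cent. The result is that "A sample number of 8 patients in each group is obtained", and then, "assuming a loss of 20%, 10 patients are calculated for each group". No other allowance is made. The section does not say what the 50% is a percentage of.
- **Inclusion and exclusion criteria.** The entry criterion is "Patients aged between 10 and 21 years with a new diagnosis of ALL" at the study hospital, with consent. The exclusions are earlier antineoplastic treatment and Down syndrome. Nothing concerns ABCB1.
- **Table 1.** Expression of each gene has three levels: none, low and high.
- **Problem statement.** ABCB1 and AMPK expression in these patients, and how it varies under treatment, is described as not yet known. No share high at diagnosis is assumed anywhere.
- **Procedures.** The high/low cut-off will come from the mean in healthy controls chosen while cases are being recruited.
- **Statistical analysis.** For expression "at the time of diagnosis and at the end of induction, McNemar's test will be used". The section also lists general two-group tests and percentages for qualitative variables. It names no conversion proportion, no confidence interval and no between-arm difference in conversion.

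**The concern.** Only a patient who is high at diagnosis can move from high to low. The trial enrols patients at any level, so the meaning of 8 per group depends on a denominator that the plan leaves open. If the source rate applies to baseline-high patients, the number per arm who can show the event is left to chance. If it applies to all patients, the 50% carries over only if the baseline-high share here resembles that in the source study, and the plan does not say that it does.

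The size is justified as estimating this proportion with 95% confidence, yet the analysis section does not undertake to estimate it. McNemar's test asks whether expression changed between two visits. It does not compare conversion between metformin and control, which is the randomised question. With the denominator unspecified, a patient who is low at both visits could be counted as a non-converter, left out, or counted as low at the end, and that choice could be made after the data are seen. In arms of 8 to 10 it can alter the result.

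**Working it through.** **Inputs.** From the Sample size section: p = 0.50, 95% confidence (z = 1.96), d = 0.05, stated n = 8 per group, 20% loss. The share high at diagnosis, h, is not in the documents. It is an assumption here and is shown over a range.

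**1. The plan's own figure.** n = z²·p·q/d² = 1.96² × 0.5 × 0.5 / 0.05² = 0.9604 / 0.0025 = 384.16, so 385 per group. The stated 8 is not reproduced. Conversely, the half-width at n = 8 is 1.96 × √(0.25/8) = 0.346, about ±35 points. The loss step does reproduce: 8/0.8 = 10.

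**2. Precision if all 8 are high at diagnosis.** The exact (Clopper-Pearson) 95% interval for 4/8 is 15.7% to 84.3%. Under the other reading, with all patients as denominator, 4 conversions among 8 patients give the same interval. Neither reading approaches ±5 points.

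**3. Patients who can show the event, if the 50% is of baseline-high patients.** The expected number among 8 evaluable is 8h. The chance of 2 or fewer is from Binomial(8, h).

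| Assumed h | Expected high among 8 | P(2 or fewer high) |
|---|---|---|
| 30% | 2.4 | 55% |
| 50% | 4.0 | 14% |
| 70% | 5.6 | 1% |
| 90% | 7.2 | not calculated |
| 100% | 8.0 | 0 |

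With 4 high and 2 converting, the exact 95% interval is 6.8% to 93.2%.

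**4. If the 50% is of all patients.** Those not high at diagnosis are non-events already included in p, and 8 patients of any baseline level is the matching denominator. Conversion cannot exceed h, so a 50% rate then requires at least half of the patients to be high at diagnosis. The plan does not state this.

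**5. Can the 8 simply be called baseline-high patients?** Expecting 8 such patients needs 8/h evaluable, divided by 0.8 for loss. This gives 27 and then 34 enrolled per group at h = 30%, 16 and 20 at 50%, and 12 and 15 at 70%. The plan enrols 10, so the relabelling would be correct only if h = 100%.

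**6. Do the planned percentages supply the conversion proportion?** Not by themselves. A fall from 5/8 high to 3/8 high fits 2 conversions with no reversals (2/5 converted) or 4 conversions with 2 reversals (4/5 converted). The paired counts are needed.

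**The case against.** The strongest reply is that the source's denominator cannot be seen. If the 50% is of all treated patients, the size does not treat every patient as able to convert, and 8 is not overstated for this reason. This stands. A reader might infer that the informative number is necessarily smaller than 8, but the documents support that only if the 50% refers to baseline-high patients and some patients are not high. A share near 100% is not excluded either.

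A reader might also infer that the sized quantity will be absent from the results. That goes too far. McNemar's test on a high/low table uses the paired high-to-low count, and the row total is the number high at diagnosis. Percentages for qualitative variables are promised, and describing expression at diagnosis is a specific objective. What is missing is a commitment to report the proportion with its interval and to compare it between arms.

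Nor is enrolment at any baseline level a defect. The hypothesis concerns mRNA level for both genes, to which low-baseline patients contribute, and the cut-off is not fixed at entry.

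Finally, 385 against 8 is the larger fault, and the added estimates will be very wide. Both are true. But correcting the arithmetic would still leave the denominator unstated and the sized proportion without a planned estimate.

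**Conclusion.** The point holds in a limited form and is worth correcting. Three things rest on the text alone: the 50% has no stated denominator, 8 patients give about ±35 points (16-84% at 4/8) against the stated 5, and no estimate, interval or between-arm difference is planned for the proportion used to set the size.

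The loss of patients who can convert is conditional. It requires the 50% to refer to those high at diagnosis, and its size (2.4 to 7.2 of 8 for shares of 30% to 90%) rests on assumed shares, since the plan gives none. The documents do not support the firmer claim that the plan overstates its informative number by a known amount. They also do not support reading the mismatch with 385 as a consequence of baseline mix: that is a separate error, and dividing 8 by the baseline-high share would not repair it.

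**What to change.** **Sample size section.** State whether the 50% is of all patients or of those high at diagnosis. Replace the 5% precision with what 8 evaluable patients per group deliver: an exact 95% interval of 16-84% at 4/8 if all are high, and 7-93% at 2/4 if half are. Give the expected number high at diagnosis over a stated range of shares, labelled as assumed. Do not relabel the 8 as baseline-high patients, and do not enrol more on this account.

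**Statistical analysis section.** Add, by arm:
- the number high at diagnosis;
- the number and proportion of these who are low or not expressed at the end of induction, with an exact 95% CI;
- the between-arm difference in that proportion, with its CI and the interval method named in advance.

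Keep all patients in the other analyses. If the 50% proves to be of all patients, the same counts also give that proportion. Because the baseline sample is taken before treatment, the baseline-high subset is defined by a pre-treatment measurement and the comparison within it keeps the benefit of randomisation.

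**Cost.** Text changes and one small table from data already collected. Eligibility, treatment, assay and enrolment do not change. The stated precision becomes much less favourable, and the baseline-high estimates will be very imprecise and should be presented as such.

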Minimal residual disease at the end of induction.	Flow cytometry measurement of the presence of 1x10 ⁻³ blasts.	Positive /Negative	Qualitative dichotomous	0: positive 1: negative
Relapse	Presence of blasts in bone marrow after remission has been achieved.	Present/absent	Qualitative dichotomous	0: absent 1: present

Time to relapse	Time from diagnosis of leukemia to relapse	Days	Quantitative	Not applicable
Death	Cessation of life	Present/absent	Qualitative dichotomous	0: absent 1: present
Time to death	Time from leukemia diagnosis to death	Days	Quantitative	Not applicable

Table 1. Variable definitions.

PROCEDURES

Patients with a newly morphological diagnosis of ALL at the Hospital General de México "[name]" will be invited to participate in this trial, and informed consent will be requested from parents and participants.

The data collection is obtained from the patients chart such as age, gender, leukocyte count, hemoglobin, platelet count and immunophenotype.

Peripheral blood samples will be collected in EDTA tube. The sample will be centrifuged obtaining mononuclear cells, and the analysis of ABCB1 and AMPK expression will be performed. This will be done on samples obtained before the start of treatment and at the end of the induction phase. Samples will be collected by peripheral vein puncture, and mononuclear cells will be separated using density gradient. Mononuclear cells are separated and suspended in PBS medium and stored at -70°C . RNA isolation is performed using TRIzol® (Invitrogen/life Technologies), and will be stored at -80°C until use. For cDNA synthesis, 2g of RNA, final volume of 20L will be combined with 200U of MMLV RT enzyme (Invitrogen, Carlsbad, CA, USA).

Expression of mRNA levels will be measured using the TaqMan gene expression assay (Applied Biosystems Foster city, CA, USA). The cut-off point between low and high expression will be determined according to mean values obtained in healthy controls, selected during case recruitment in a 2:1 ratio for each case.

Regarding treatment, patients will be randomized into 2 groups, where in both cases the conventional remission induction treatment will be given, and to intervention group metformin will be added at a dose of 1000mgm2Seday, divided into two doses, with a maximum dose of 850mg every 8 hour, orally.

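### The sample size comes from a one-proportion precision formula, so 8 per group is not a size for the randomised comparison, and it does not follow from that formula's own inputs

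*Combined protocol and SAP*

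**What the plan says.** The specific objectives include comparing ABCB1/MDR1 and AMPK expression "at diagnosis and at the end of induction in adolescents with ALL treated with conventional chemotherapy and those additionally treated with metformin". Under Procedures, "patients will be randomized into 2 groups, where in both cases the conventional remission induction treatment will be given", and only the intervention group receives metformin. The comparator is therefore concurrent chemotherapy alone.

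The Sample size section takes its single rate from a cited publication, in which "a decrease in the expression pattern of ABCB1 gene expression from high to low expression after metformin administration was 50" per cent. It then states: "The sample size calculation was based on the formula for estimating a proportion, with a confidence level of 95% and a precision of 5" per cent, and prints n = Z²pq/d². It reports 8 per group, raised to 10 for a 20% loss.

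Statistical Analysis gives no power or target difference. For expression at diagnosis against the end of induction it names McNemar's test, a within-patient test. Fisher's exact test appears only in a general list for bivariate analysis.

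The Hypothesis section predicts a fall in ABCB1 and a rise in AMPK.

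**The concern.** In a randomised trial with a shared chemotherapy backbone, the effect of metformin is the difference between the arms. Both arms receive the same induction drugs between the two expression samples, and the Problem Statement says that how expression varies during treatment is not known. Some conversion on chemotherapy alone is therefore possible, and a conversion rate in the metformin arm cannot by itself be credited to metformin.

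The sizing deals only with how precisely one proportion is estimated. A reader who sees a calculated 8 per group will take it as adequate for the randomised question, when nothing in the calculation bears on that question. At stake is how the result is read: an uninformative comparison could be presented as if the trial had been sized to answer it.

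**Working it through.** **1. The plan's own figure.** Inputs from the Sample size section: p = 0.50, q = 0.50, d = 0.05, 95% confidence (z = 1.96).

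- n = 1.96² × 0.5 × 0.5 / 0.05² = 384.1, so 385, not 8.
- Solving for d at n = 8: 1.96 × √(0.25/8) = 0.346. As a check, d = 0.35 gives 1.96² × 0.25 / 0.35² = 7.84, so 8.
- A one-sided z gives 271.
- The loss step is right: 8 / (1 − 0.2) = 10.

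**2. What the size gives for one arm.** The 95% half-width at 50% is 1.96 × √(0.25/8) = 0.35 with 8 evaluable and 1.96 × √(0.25/10) = 0.31 with 10.

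**3. What it gives for the comparison.** Conversion on metformin is 50% (the plan's figure); the test is two-sided Fisher at 5%. The plan gives no control rate, so a range is assumed. These figures also assume that every patient is high at diagnosis and so able to convert.

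The 0% control case can be done by hand.

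- 8 per arm: 4/8 against 0/8 gives p = 2 × C(8,4)/C(16,4) = 140/1820 = 0.077; 5/8 against 0/8 gives p = 0.026. Five converters are needed, and P(X ≥ 5 | 8, 0.5) = 93/256 = 36%.
- 10 per arm: 5/10 against 0/10 gives p = 2 × C(10,5)/C(20,5) = 504/15504 = 0.033, while 4/10 gives 2 × C(10,4)/C(20,4) = 420/4845 = 0.087. Again five are needed, and P(X ≥ 5 | 10, 0.5) = 638/1024 = 62%.

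The other rates come from enumerating all 2×2 tables:

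| Assumed control conversion | Power, 8 per arm | Power, 10 per arm |
|---|---|---|
| 0% | 36% | 62% |
| 5% | 28% | 43% |
| 10% | 22% | 30% |
| 20% | 12% | 13% |
| 30% | 6% | 5% |

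Even at 0% control, 80% exact power needs 12 evaluable per arm. With 8 per arm, 80% power needs metformin conversion of about 70%, 81% or 91% against 0%, 10% or 20% on control.

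**4. Who can convert.** Table 1 codes expression as none, low or high, and Procedures sets the cut-off from the healthy-control mean. Only patients high at diagnosis can go from high to low. Treat 50% as a rate among them, let the number high in each arm vary binomially, and test among them only. At 0% control, power for 8 to 10 evaluable per arm is then:

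| Assumed share high at diagnosis | Power |
|---|---|
| 100% | 36–62% |
| 70% | 21–36% |
| 50% | 11–18% |

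**The case against.** The strongest defence is that 8 is not arbitrary. A two-proportion formula with unpooled variance, for 50% against 0%, two-sided 5% and 80% power, gives (1.96 + 0.84)² × (0.25 + 0) / 0.5² = 7.84, so 8. A reader might infer that the plan really assumed no conversion on chemotherapy alone. The documents do not support this. They print the one-proportion formula, enter 50% as p and never as a between-arm difference, and state neither a control rate nor a power. The approximation is also poor at this size: pooled variance gives 11 per group, and exact power at 8 is 36%.

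It can also be said that p = 0.5 maximises pq and is therefore the cautious input for estimating either arm's proportion, whatever the control rate. That is true, but precision per arm is not power for a contrast.

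Three further points stand and limit what can be claimed.

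- The denominator behind the cited 50% cannot be seen from these documents, so no single power figure can be called the trial's power.
- The documents do not say that the metformin arm will be judged against 50%, or that a non-significant difference will be read as no effect. Those are risks of interpretation, not stated intentions.
- They give no feasibility reason for the number, so one should not be supplied on the sponsor's behalf.

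A defence that this is only a pilot fails: the protocol does not call it one, and its general objective is to evaluate efficacy.

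**Conclusion.** The point holds. The stated size is wrong as written in two separate ways: it belongs to a one-group estimation problem, and it does not follow from the formula and inputs given (385 against 8). Correcting the precision to about 35 points would cure the second fault and leave the first.

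The conclusion on power does not hang on the assumed control rate. At 0%, the most favourable case, exact power is 36% with 8 evaluable per arm and 62% with 10; at 20% it is 12% and 13%. These figures rest on 50% conversion on metformin, a two-sided 5% Fisher test, and every patient being high at diagnosis. They are upper values because of the last assumption. No figure can be given for AMPK, since the plan states no rate for it.

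A reader might infer that the randomised design is unsound or that the trial must be enlarged. Neither follows. The comparison is legitimate, but the plan should present it as exploratory and say how little it can detect.

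**What to change.** Keep 10 per group.

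**Sample size section.**
- Delete the statement that 8 per group results from the one-proportion formula at 5% precision.
- State what 8 to 10 evaluable per arm provides: a 95% half-width of about 31–35 percentage points for an arm's proportion at 50%, and low power for the between-arm contrast.
- Give that power as at most about 36–62% at 0% control conversion and 12–13% at 20%, label the control rates as assumptions, and add that at 0% control it falls to about 21–36% or 11–18% if 70% or 50% of patients are high at diagnosis.
- Give a feasibility reason only if the sponsor has one.

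**Effect definition.** Define the metformin effect as the metformin-minus-control difference in change: ABCB1 high-to-low conversion among patients high at diagnosis, and the corresponding increase for AMPK.

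**Statistical Analysis section.**
- Assign the already listed Fisher's exact test to this between-arm comparison, and keep McNemar's test as a within-arm description.
- Report the difference with a confidence interval.
- Describe the trial as exploratory for this objective, and say that a non-significant difference will not be read as no effect.

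**Cost.** Edits to two sections and a short definition, with no extra patients, samples or procedures. The downside is a less favourable stated justification. Any separate correction of the formula's arithmetic should be made in the same edit.

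### The stated formula and 5% precision cannot give 8 per group: with z = 1.96 they give 385 at p = 50% and at least 16 for any p from 1% to 99%

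*Combined protocol and SAP*

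**What the plan says.** Under METHODOLOGY, Sample size, the plan cites a publication in which the change in ABCB1 expression "from high to low expression after metformin administration was 50" per cent. It does not label this figure as p. It then says that the calculation was "based on the formula for estimating a proportion, with a confidence level of 95% and a precision of 5" per cent, and prints the single-proportion formula n = Z²pq/d². The result follows directly: "A sample number of 8 patients in each group is obtained, assuming a loss of 20%, 10 patients are calculated for each group". No other p or d, no power, no control rate and no finite-population correction appears anywhere in the document.

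Two other sections bear on the point. The specific objectives include comparing expression at diagnosis and "at the end of induction in adolescents with ALL treated with conventional chemotherapy and those additionally treated with metformin", which is a comparison between arms. Under PROCEDURES, high and low expression are separated by healthy-control values: "The cut-off point between low and high expression will be determined according to mean values obtained in healthy controls". The number of patients who will start with high expression is therefore not known in advance, and the plan does not estimate it.

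**The concern.** The formula, the confidence level, the precision and the result stand next to each other and do not agree. For an outcome proportion anywhere near 50%, a margin of ±5 points needs hundreds of patients, so a single-digit answer signals that some other input or method was used.

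This is the only justification of the sample size in the document. As written, it promises ethics and research committees a precision that 8 or 10 patients per group cannot give, and it hides what produced 8. It also leaves the comparison of metformin with conventional treatment without any stated sizing, because the formula has no term for a difference between groups.

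**Working it through.** **Inputs.** All come from the Sample size section: 95% confidence (z = 1.96, two-sided), d = 0.05, an outcome proportion of 50%, a stated result of 8, and 20% loss.

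**1. The plan's own figures.** The loss allowance reproduces: 8 / 0.8 = 10. The 8 itself does not:

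n = 1.96² × 0.5 × 0.5 / 0.05² = 384.16, rounded up to 385.

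**2. Does another p rescue it?** The 50% is not labelled as p, so p was varied with d held at 0.05. The product p(1 − p) is smallest at the ends of the range, so the minimum over 1% to 99% lies at those two values.

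| p | n from formula | rounded up |
|---|---|---|
| 50% | 384.1 | 385 |
| 10% or 90% | 138.3 | 139 |
| 5% or 95% | 73.0 | 73 |
| 1% or 99% | 15.2 | 16 |

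Solving for n = 8 gives p(1 − p) = 8 × 0.0025 / 3.8415 = 0.0052, so p = 0.52% or 99.48%.

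**3. Does another reading rescue it?**
- One-sided z = 1.645: 271 at p = 50%, and a minimum of 11 over 1% to 99%.
- Relative precision, d = 0.05 × 0.5 = 0.025: 1,537.
- Finite-population correction, n₀ / (1 + (n₀ − 1)/N) with n₀ = 384.15: 7.86 for N = 8 and 8.82 for N = 9. It gives about 8 only if the whole population is 8 or 9, which is not documented.

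**4. Routes that do reach 8, none of them stated.**
- p = 0.5 with d = 0.35: 3.8415 × 0.25 / 0.1225 = 7.84.
- Unpooled comparison of 50% with 0%, two-sided 5%, 80% power: (1.960 + 0.842)² × (0.5 × 0.5 + 0 × 1) / 0.5² = 7.85.

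Two unrelated methods reach the same number, so 8 does not reveal how it was obtained.

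**5. Precision delivered for one arm near 50%.** The half-width is 1.96 × √(0.25/n), shown beside the exact (Clopper-Pearson) 95% interval.

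| n | half-width | exact interval |
|---|---|---|
| 10 | ±31 points | 18.7% to 81.3% (5/10) |
| 8 | ±35 points | 15.7% to 84.3% (4/8) |
| 6 | ±40 points | 11.8% to 88.2% (3/6) |
| 4 | ±49 points | 6.8% to 93.2% (2/4) |

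Against the claimed 5 points, 0.310/0.05 = 6.2 and 0.346/0.05 = 6.9. The rows for 6 and 4 are illustrations only. They show what happens if just the patients with high baseline expression form the denominator, since only they can move from high to low.

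**6. Precision for the difference between arms (Newcombe 95% interval).**
- 4/8 vs 4/8: ±40.3 points. 5/10 vs 5/10: ±37.3 points.
- 4/8 vs 0/8: 6.8 to 78.5 points, half-length 35.8.
- 5/10 vs 0/10: 11.7 to 76.3 points, half-length 32.3.

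The document gives no control rate. With one arm at 50% and the other anywhere from 0% to 100%, the half-length runs from 36 to 40 points with 8 per group and from 32 to 37 with 10.

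**The case against.** Five objections can be made.

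- **Sidedness.** The plan writes Z with subscript alpha and does not say that it is two-sided, so the floor of 16 depends on z = 1.96. This is correct as a condition, and it is stated here. It does not alter the conclusion, because one-sided z still gives 11 at the least and 271 at 50%.
- **Another method may have been used.** This is possible, but the document names the formula and its inputs and says that 8 follows from them. The alternatives in step 4 are conjecture and should not be read as what the sponsor did.
- **The denominator of the 50%.** The plan's sentence could describe conversion among patients who started high, change among all patients, or a fall in the share with high expression. The cited source is not available to settle this. The objection stands to the extent that the warning about high-baseline patients must stay conditional.
- **The between-arm interval.** The Statistical Analysis section plans McNemar's test for change over time and names between-group tests only generically, and the variable table gives expression three categories. A high-to-low difference between arms is therefore one choice of summary among several. This is fair: the interval is a useful addition and can be separated from the correction of the false statement.
- **Small exploratory trials are legitimate.** They are, and nothing here disputes the planned size. What fails is the reason given for it.

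**Conclusion.** The concern holds, and the text must be corrected. The plan's formula, confidence level and precision do not yield 8 for any p from 1% to 99%, whichever sidedness is assumed. With z = 1.96 they yield 385 at 50% and at least 16 elsewhere in that range. The error lies in the step from the formula to 8; the allowance for losses is sound.

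The precision figures assume a proportion near 50% and count every evaluable patient in the arm. The illustrations with fewer patients and the between-arm figures rest on assumed counts that the document does not supply. Confidence in the core contradiction is high, since it rests only on figures printed in one section.

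**What to change.** Rewrite the Sample size paragraph as follows.

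1. Delete the claim of 5% precision.
2. State the formula, p and d actually used to reach 8, or the power and control rate if it came from a comparison.
3. State the precision that the size delivers for a single-arm proportion near 50%: about ±35 points with 8 evaluable (exact 95% interval 15.7% to 84.3% for 4/8) and ±31 points with 10 (18.7% to 81.3% for 5/10). Add that it will be wider if only patients with high baseline expression form the denominator.
4. Say that the single-proportion formula does not size the comparison between arms and, only if true, that no power calculation was done.
5. Report the between-arm difference with a small-sample interval such as Newcombe's, noting about ±40 points with 8 and ±37 with 10 per group at 50% in both arms. This item can be decided separately from items 1 to 4.

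The cost is one paragraph and one reported interval. The drawback is a less favourable stated precision. No change in planned numbers is required; the basis for 10 per group is for the sponsor to state.
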